7.8 Withdrawal criteria

There will be intention-to-treat analyses carried out. Analysis of all participants who have been randomised will be undertaken regardless of withdrawal. The reason for withdrawal will

be recorded in the CRF. Each participant has the right to withdraw study at any time. A participant will be withdrawn from the study if any of the following occurs:

- Absence of anaemia on postoperative days 2, 3 and 5.
- Pregnancy
- Ineligibility (either arising during the study or retrospective having been inadvertently overlooked at screening)
- Significant protocol deviation as defined by the CI
- An adverse event which requires discontinuation of the study medication or results in inability to continue to comply with study procedures
- Disease progression which requires discontinuation of the study medication or results in inability to continue to comply with study procedures
- Patients who do not undergo an operation as a result of a change in fitness for surgery will be excluded.
- Consent withdrawn.
- Lost to follow up

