6.2 Exclusion criteria

- Patients with mental health issues or learning disabilities resulting in their inability to consent to the study

- Patients who do not have a histological diagnosis of colorectal adenocarcinoma
- Female participants who are pregnant, lactating or planning a pregnancy during the course of the study.
- Patients with evidence of iron overload or disturbances in utilisation of iron as stated in the product SPC.
- Previous gastric, small bowel or colorectal surgery (where ≥50% of stomach or terminal ileum has been resected)
- Chemotherapeutic treatment within the last 4 weeks.
- Known previous anaemia not attributable to colorectal carcinoma (i.e. anaemia in patients with well established, inflammatory disorders)
- Known haematological disease.
- Features necessitating urgent surgery (e.g. obstructive symptoms).
- Previous allergy to intravenous or oral iron or related iron products.
- Patients who are unable to consent.
- Any other significant disease or disorder which, in the opinion of the Investigator, may either put the participants at risk because of participation in the study, or may influence the result of the study, or the participant's ability to participate in the study.
- Participants who have participated in another research study involving an investigational product in the past 12 weeks
- Confirmed liver or lung metastases

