9.1.5 Expected Serious Adverse Events/Reactions

Serious adverse events that could be expected during the course of the study according to the SmPC include vomiting, haematemesis, gastrointestinal perforation, abdominal pain and dysphagia which could be related to the progression of the disease. Adverse events may also be anticipated in relation to any postoperative chemotherapy used. These would include anaemia, neutropenia (and consequences of sepsis), thrombocytopenia (and consequences of

coagulopathy), rashes, photosensitivity, taste/hearing disturbance, hair loss, discoloured urine, diarrhoea, oral ulceration and renal failure. These adverse events will be recorded in the CRF as significant clinical events.

Events which are not deemed secondary to the underlying cancer will be reported to the sponsor as a Serious Adverse Event within 24 hours of the Investigator becoming aware of the event.

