16. APPENDICES

16.1 Appendix 1 – Schedule of Procedures

Procedures	Screening	Baseline	Treatment Phase				Follow Up
	Visit 1	Visit 2	Visit 3 Day of surgery	Visit 4 Day2	Visit 5 Day 3	Visit 6 Day 5	Vist 7 8-12 weeks
Screening	X						
Informed consent		X					
Demographics		X					
Medical history		X					
Concomitant medications		X					
Eligibility assessment	X						
Randomisation			X				
Dispensing of trial drugs				(X)	(X)	(X)	
Blood Sample		X	X	X	X	X	X
Urine Sample*		X	X	X	X	X	X
Tumour Sample			X				
Paraffin embedded sections							X at a later date
Faeces/stool sample*		X	X	X	X	X	X
Saliva sample*		X	X	X	X	X	X
Sweat sample*		X	X	X	X	X	X
QoL questionnaire completion		X	X				X
Grip Strength			X	X	X	X	X
Adverse event assessments		X	X	X	X	X	X
CRF Data collection		X	X	X	X	X	X
Physician's Withdrawal Checklist		X	X	X	X	X	X

*If consented for sample sub-study.

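### Section 7.8 sets no cut-off for withdrawal on ineligibility; read literally, the undated chemotherapy and metastasis exclusions become post-randomisation withdrawal rules and lower the primary retention outcome

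*Combined protocol and SAP*

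**What the plan says.** Section 7.8 introduces its list with "A participant will be withdrawn from the study if any of the following occurs". One bullet is "Ineligibility (either arising during the study or retrospective having been inadvertently overlooked at screening". It names no criteria and no time limit such as randomisation or surgery.

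Two of the exclusions in section 6.2 can become true later and have no reference date: "Chemotherapeutic treatment within the last 4 weeks" and "Confirmed liver or lung metastases".

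Two other places bear on the same patients:

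- Section 9.1.5: "Adverse events may also be anticipated in relation to any postoperative chemotherapy used". After listing such events it adds: "These adverse events will be recorded in the CRF as significant clinical events". It does not mention withdrawal.
- A separate bullet in 7.8 covers "Disease progression which requires discontinuation of the study medication or results in inability to continue to comply with study procedures".

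Appendix 1 ticks the row "Eligibility assessment" at Visit 1 only and randomisation at Visit 3, the day of surgery. It schedules a physician's withdrawal checklist at Visits 2 to 7. Section 10.3.2 lists retention and patient withdrawal among the primary feasibility outcomes and labels withdrawal as non-concordance.

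**The concern.** Entry criteria normally describe a patient at one moment. The 7.8 bullet treats criteria missed at screening as a separate case, so its other half must mean criteria that become true afterwards. With no end point, that half reaches to the final visit at 8-12 weeks. A randomised patient who starts chemotherapy after surgery, or has a liver or lung metastasis confirmed, would have to leave the study even if still willing and able to attend.

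At stake is what the feasibility figures mean. Sections 3.3.1 and 10.2 use the trial's data to plan a definitive trial. A withdrawal caused by the protocol's own wording would be counted alongside patients who chose to stop, and haemoglobin and quality-of-life data after that point might not be collected. Staff who applied 7.8 literally and staff who followed 9.1.5 would record different retention for the same patient.

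**Working it through.** **Step 1: the passages side by side.**

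| Event after randomisation | Ineligibility bullet in 7.8, read literally | Other text |
|---|---|---|
| Chemotherapy starts before the final visit | Withdraw from the study | 9.1.5: record its adverse events in the CRF; withdrawal not mentioned |
| Liver or lung metastasis confirmed | Withdraw from the study | 7.8 progression bullet: withdraw only if study medication must stop or study procedures cannot be followed |

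In the second row, two bullets of one list give different answers for a patient who can continue both medication and visits.

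**Step 2: does the rule operate during follow-up?** The withdrawal checklist in Appendix 1 runs to Visit 7, so withdrawal is considered at every postoperative visit. The checklist's content is not shown.

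**Step 3: the plan's own figure.** Section 10.1 gives 40 patients, 20 per arm: 2 × 20 = 40. No sample size calculation is performed, so only this sum can be reproduced.

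**Step 4: effect on retention.** Section 10.3.2 defines no denominator; I take the 40 as randomised (assumption). One withdrawal costs 1/40 = 2.5 percentage points. Let c be the share withdrawn for chemotherapy or new metastases. The documents give no value for c and no timing of chemotherapy relative to the final visit, so the range below is assumed. With no other loss, retained = 40 × (1 − c):

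| c (assumed) | Retained of 40 | Retention | Wilson 95% interval |
|---|---|---|---|
| 0% | 40 | 100% | 91.2-100% |
| 10% | 36 | 90% | 76.9-96.0% |
| 20% | 32 | 80% | 65.2-89.5% |
| 30% | 28 | 70% | 54.6-81.9% |
| 40% | 24 | 60% | 44.6-73.7% |
| 50% | 20 | 50% | 35.2-64.8% |

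**Step 5: against the plan's own benchmark.** Section 10.1 regards 30 or more patients as enough to estimate a parameter. Fewer than 30 remain once c exceeds 1 − 30/40 = 25%. Section 7.8 also withdraws patients without postoperative anaemia. Section 1 puts postoperative anaemia at up to 90%, so as a scenario take 10% as not anaemic: 40 × 0.9 = 36 remain, and the number falls below 30 once c exceeds 1 − 30/36 = 16.7%.

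**The case against.** The strongest reply is that the literal reading was probably not intended. Section 7.8 names neither chemotherapy nor metastases. Pregnancy is an exclusion in 6.2 yet has its own withdrawal bullet, and progression has its own narrower one. If the ineligibility bullet swept in every entry exclusion, the first would be redundant and the limits in the second pointless. Read literally, the exclusion for earlier bowel resection could even be met by the trial operation itself. The bullet may be meant only for the interval from consent to surgery, and 9.1.5 supports that. This stands: the conflict is an unresolved ambiguity, a contradiction only on the literal wording. But nothing in the text fixes the narrower reading, and the rule is mandatory.

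Section 7.8 also analyses all randomised participants whether or not they withdraw, and records the reason for withdrawal, so causes could be separated afterwards. Section 3.3.1 sets no feasibility threshold, so no decision turns on the rate. Both are true. Neither recovers data not collected: no visits are provided for after withdrawal for ineligibility (9.2 provides an end-of-study assessment only when an adverse event ends participation), and 10.5 excludes a participant whose missing data cannot be recovered or re-sampled.

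A reader might infer more than the documents support:

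- **That chemotherapy is expected.** Section 9.1.5 only foresees events from any that is used.
- **That retention will in fact be depressed by a known amount, or that the remaining patients are lower-stage.** No rate, timing or stage mix is given.
- **That sites would diverge.** Sections 4 and 5 make the trial single-centre; only staff or readings could differ.
- **That a breach between consent and surgery is found only after allocation.** The withdrawal checklist at Visits 2 and 3, the eligibility check before consent (7.2) and the day-of-surgery interview (7.7) could find it earlier. What is missing is a stated confirmation before randomisation.

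**Conclusion.** The point holds as a wording conflict with a conditional effect on a primary outcome. The withdrawal rule has no cut-off, the two exclusions have no reference date, and the literal result disagrees with 9.1.5 and with the progression bullet. On that reading each affected patient lowers retention by 2.5 percentage points and is classed as non-concordant for a reason that has nothing to do with willingness or adherence.

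The total effect is unknown. The 90-50% range rests on three assumptions: 10-50% affected, 40 randomised as the denominator, and no other loss. If the narrower reading is intended, chemotherapy or metastases arising after surgery cost nothing in retention. The timing of randomisation is itself unsettled: section 4 and Appendix 1 place it before the operation or on its day, while section 7.7 places it postoperatively. Whether a metastasis found at surgery counts as post-randomisation therefore cannot be determined. The matter should be corrected, but it does not undermine the trial.

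**What to change.** - Reconcile 6.2, 7.8 and 9.1.5: state the reference time, for example randomisation, at which each time-dependent exclusion applies, and make the ineligibility and progression bullets agree.
- In 7.8, separate stopping study treatment from leaving the study, so that randomised participants are still followed to the 8-12 week visit unless they withdraw consent. Whether chemotherapy or new metastases should stop study treatment is for the sponsor to decide.
- In 10.3.2, report withdrawals required by a protocol rule separately from non-concordance, and state the retention denominator.
- Settle whether randomisation is preoperative (section 4) or postoperative (section 7.7), then add an eligibility confirmation immediately before it in Appendix 1. A criterion breached before allocation would then count as a screen failure.

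The cost is a few sentences and one extra tick in the schedule, with no new visit or test. A small downside is that follow-up data will include any patients on chemotherapy, so haemoglobin will be more variable.

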7.3 The Randomisation scheme

Randomisation will be undertaken via an online platform in a 1:1 fashion to either the control group (standard care) or the intervention group (postoperative ferric maltol). The study will be an open label design and participants will be informed of their group allocation after their operation. Randomisation alerts with allocation details will be emailed to the CI, research fellow, research nurses and the pharmacy team.

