7.4 Blinding

Patient and investigator will not be blinded to the study treatment allocation due to the change in stool colour with oral iron intake. It is not possible to simulate this change with a placebo “dummy” drug for the control group.

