8.8 Assessment of compliance with treatment

Participants will self-administer the oral ferric maltose tablets. Patients will be asked to declare their compliance with the study drug during the final follow up study visit. If there is a high level of non-compliance (<70%), the patient will be included in the trial under the intention-to-treat-analysis. The reasons for non-compliance will be documented in the CRF.

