13.3 Protocol compliance

Protocol non-compliances will be defined as departures from the approved protocol.

Prospective, planned deviations or waivers to the protocol are not allowed under the UK regulations on Clinical Trials and must not be used e.g. it is not acceptable to enrol a participant if they do not meet the eligibility criteria or restrictions specified in the trial protocol. Accidental protocol deviations will be adequately documented on the relevant protocol deviation form and reported to the Chief Investigator and Sponsor immediately. Deviations from the protocol which are found to frequently recur are not acceptable, will require immediate action and could potentially be classified as a serious breach.

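### Section 7.8 withdraws randomised participants for an undefined significant deviation, at the discretion of a chief investigator who knows the allocation, and no section says follow-up continues

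*Combined protocol and SAP*

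**What the plan says.** Section 7.8 opens with an intention-to-treat commitment: "Analysis of all participants who have been randomised will be undertaken regardless of withdrawal". It then lists events that lead to withdrawal from the study, one of which is "Significant protocol deviation as defined by the CI".

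Other sections bear on that bullet:

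- **7.3 and 7.4 (allocation and blinding).** "Randomisation alerts with allocation details will be emailed to the CI, research fellow, research nurses and the pharmacy team". The trial is open label: "Patient and investigator will not be blinded to the study treatment allocation due to the change in stool colour with oral iron intake".
- **8.8 (compliance).** "Patients will be asked to declare their compliance with the study drug during the final follow up study visit". Where compliance is below 70%, "the patient will be included in the trial under the intention-to-treat-analysis".
- **13.3 (deviations).** "Protocol non-compliances will be defined as departures from the approved protocol". No threshold is set for a significant one. "Accidental protocol deviations will be adequately documented on the relevant protocol deviation form and reported to the Chief Investigator and Sponsor immediately". The section does not say whether the participant stays in the study.
- **10.5 (missing data).** If data cannot be recovered and a blood test cannot be repeated, the participant is excluded from the trial.
- **10.3.2 (primary outcomes).** Withdrawal, compliance with the randomised treatment, retention and completion of outcome measures are all primary feasibility measures.

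**The concern.** The bullet is a removal rule that acts after randomisation, has no criteria fixed in advance, and is applied by someone who knows the arm. Two things are at stake.

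First, an intention-to-treat analysis needs outcomes as well as a list of those randomised. If withdrawal from the study ends data collection, the final haemoglobin, haematinics and quality-of-life scores at 8-12 weeks are missing for that participant, and 10.5 then points to exclusion.

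Second, retention and withdrawal are part of the primary result. Section 3.3.1 sets no feasibility criteria in advance and says the data will determine the sample size of a definitive trial. A retention figure that partly reflects one person's judgement about deviations is a poor guide to the attrition that trial should expect.

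**Working it through.** The plan gives no figure to reproduce on this point; section 10.1 states that no sample size calculation is performed. The check is mainly a comparison of sections, with simple arithmetic for scale.

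**1. Is the rule defined?** 7.8 leaves it to the chief investigator. 13.3 treats any departure from the protocol as non-compliance and does not grade it. So any departure could be classed as significant.

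**2. Does follow-up continue?** Section 9.2 provides an end-of-study assessment for participants who leave treatment because of an adverse event. No section provides one after a deviation withdrawal. Appendix 1 lists a withdrawal checklist at each visit from baseline on, but its content is not given. The documents neither stop nor continue data collection.

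**3. What follows if final data are missing?** 7.8 says analyse everyone randomised; 10.5 says exclude when missing data cannot be recovered. For a participant withdrawn before the 8-12 week visit, both rules can apply and they give opposite answers.

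**4. When can a deviation come to light?** Appendix 1 shows no visit between Day 5 and the 8-12 week visit, and compliance is declared at that last visit, where final bloods and questionnaires are taken (7.7). A withdrawal for self-declared poor compliance would therefore usually come once outcomes are in hand. The risk of losing data comes mainly from deviations identified earlier, for example during the inpatient stay.

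**5. Which arm is exposed?** Dosing and drug-spacing rules (8.5, 8.6) apply only to ferric maltol; controls receive standard care (8.1). Visits, samples, questionnaires and stopping existing oral iron (8.7) apply to both.

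**6. Scale.** Input: 20 per arm, 40 in total (10.1). The number withdrawn, k, is an assumption; the documents give no rate. Retention is taken over all 20 randomised.

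- One withdrawal: 1/20 = 5 percentage points in the arm; 1/40 = 2.5 points overall.
- k = 2: 18/20 = 90% (exact 95% confidence interval 68% to 99%); overall 38/40 = 95%.
- k = 4: 16/20 = 80% (56% to 94%); overall 36/40 = 90%.
- Carried into a definitive trial as an attrition allowance, 90% retention inflates the sample by 1/0.90 = 1.11 and 80% by 1/0.80 = 1.25.
- Upper bound on selection: if those withdrawn were the k lowest of 20 normally distributed outcomes and were left out of the analysis, simulation puts the shift in the arm mean at about 0.10 SD (k = 1), 0.18 SD (k = 2) or 0.33 SD (k = 4). Nothing in the documents suggests that this worst case would occur.

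**The case against.** The strongest reply is that 7.8 already protects the analysis, that the chief investigator's knowledge of allocation simply follows from a justified open-label design, and that a descriptive feasibility study has little to bias. Much of this stands, and it rules out four stronger readings that a reader might infer.

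- **That participants are removed from the analysis.** 7.8 says the reverse. The loss is indirect, through outcomes not collected and the exclusion rule in 10.5. Transfusion and hospital-record data (11.1) might still be available.
- **That removals would fall almost only on ferric maltol.** Controls can also deviate (step 5). In addition, 8.5 itself provides for late doses within 6 hours and for restarting after an interruption, so these are not deviations in themselves. The documents give no rates for either arm.
- **That 7.8 contradicts 8.8.** The opening of 7.8 and 8.8 agree on intention to treat. A clash arises only if the chief investigator classes compliance under 70% as significant, which the text permits but does not say. Nor does 13.3 promise retention; it is silent, and asks for immediate action on recurring deviations.
- **That the rule would favour ferric maltol.** The timing in step 4 largely removes the route by which poor adherers would be dropped before their outcomes are measured.

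It can also be said that defining the term in advance would be enough. That would cure the discretion, but would still end participation for a reason that 8.8, in the case of poor compliance, treats as no bar to staying in. What the reply does not answer is the missing follow-up provision and the conflict between 7.8 and 10.5.

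**Conclusion.** The point holds in a limited form and should be acted on. Section 7.8 contains an undefined withdrawal rule, applied after randomisation by someone who knows the allocation. With no stated follow-up and with 10.5 as written, it can lose final outcomes and undercut the section's own intention-to-treat statement. It also makes two primary feasibility measures partly discretionary, at 5 percentage points of arm retention per case.

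The conclusion about lost outcomes assumes that withdrawal from the study ends data collection, which the documents leave open, and that some deviations are identified before the 8-12 week visit. The retention figures of 80% to 90% rest on an assumed 2 to 4 withdrawals in an arm. Some imbalance between arms is plausible; its size and the direction of any bias are not established.

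**What to change.** - Delete the deviation bullet from 7.8.
- State there that protocol deviations, including non-compliance at any level, are logged and reported under 13.3 and do not end follow-up or data collection. The participant attends the 8-12 week visit unless consent is withdrawn.
- Report deviations by arm as a separate feasibility result.
- Reconcile 10.5 with 7.8, so that missing data do not remove a randomised participant from the intention-to-treat population.

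These changes concern study participation and data collection only; they leave decisions about treatment where they are. The cost is one deletion, a sentence or two in 7.8, a small table and an edit to 10.5, with no extra visits or staff. The downside is small: the haemoglobin contrast includes poor adherers, as 8.8 already accepts.

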If a patient is found to be not anaemic on day 2 postoperatively (Hb \geq 130g/L men, \geq 120g/L women) they will complete screening and remain in the study but will not enter their allocated treatment pathway (i.e ferric maltol or standard care). If they remain anaemic on day 3 or day 5 blood tests they will, at this stage, enter their allocated treatment pathway. If patients have a normal haemoglobin on days 2, 3 or 5 they will be withdrawn from the study.

Outpatient Follow Up

Finally, after discharge the patient will be seen in their first outpatient clinic at 8-12 weeks postoperatively. Where follow up occurs earlier, for example, due to the clinician's normal practice or due to a complication, then the usual 8-12 week outpatient visit will still be used.

At this visit the following assessments will be undertaken

- Information regarding postoperative complications, the length of hospital stay and readmissions to hospital will be documented in the CRF
- Any postoperative transfusion requirements will be documented in the CRF.
- Blood will be drawn for the following tests: Full blood count, erythropoietin, C-reactive protein, iron, ferritin, transferrin, transferrin saturation
- Optional sub-study urine, stool, saliva and sweat samples may be taken for analyses
- Grip strength may be recorded
- The participant will be requested to complete Quality of Life questionnaires: SF36, EQ-5D and FACT- An questionnaires.

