8 TRIAL TREATMENTS

8.1 Name and description of the medicinal product

The study intervention treatment is oral ferric maltol (Feraccru®). The recommended dose is one 30mg capsule twice daily, morning and evening, on an empty stomach. Feraccru is indicated in adults for the treatment of iron deficiency. No dose adjustment is needed in elderly patients or patients with renal impairment (eGFR ≥ 15 ml/min/1.73 m²). The control group will receive standard care only. Any treatments will be at the discretion of the patient's usual clinical team. The study treatments will be randomly allocated in a 1:1 fashion but there will be no blinding of the treatment

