9.2 Recording and reporting of SAEs, SARs AND SUSARs

All AEs occurring during the study observed by the investigator or reported by the participant, whether or not attributed to study medication, will be recorded on the CRF. These adverse events will be recorded in the CRF. All SAEs assigned by the PI or delegate (or following central review) as both suspected to be related to IMP-treatment and unexpected will be classified as SUSARs and will be subject to expedited reporting to the Medicines and Healthcare Products Regulatory Agency (MHRA). The sponsor will inform the MHRA, the REC and Marketing Authorisation Holder (if not the sponsor) of SUSARs within the required expedited reporting timescales. All related AEs that result in a participant’s withdrawal from the study or are present at the end of the study, will be followed up until a satisfactory resolution occurs.

It will be left to the investigator’s clinical judgment whether or not an AE is of sufficient severity

to require the participant's removal from treatment. A participant may also voluntarily withdraw from treatment due to what he or she perceives as an intolerable AE. If either of these occurs, the participant will undergo an end of study assessment and be given appropriate care under medical supervision until symptoms cease or the condition becomes stable.

The severity of events will be assessed according to the Common Terminology Criteria for Adverse Events (CTCEA V 5.0) the following scale:

- Grade 1 Mild; asymptomatic or mild symptoms; clinical or diagnostic observations only; intervention not indicated.
- Grade 2 Moderate; minimal, local or non-invasive intervention indicated; limiting age appropriate instrumental ADL.
- Grade 3 Severe or medically significant but not immediately life-threatening; hospitalization or prolongation of hospitalization indicated; disabling; limiting self-care ADL.
- Grade 4 Life-threatening consequences; urgent intervention indicated.
- Grade 5 Death related to AE

The relationship of AEs to the study medication will be assessed by a medically qualified investigator. Any pregnancy occurring during the clinical study and the outcome of the pregnancy, will be recorded and followed up for congenital abnormality or birth defect.

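### Section 7.8 makes stopping study medication for an adverse event or progression a withdrawal from the study, a route open only to the ferric maltol arm, and nothing visible secures those participants' 8–12 week bloods and questionnaires beyond an undefined assessment after adverse-event stops

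*Combined protocol and SAP*

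**What the plan says.** All references are to the combined protocol and SAP.

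- **Section 7.8** lists events that take a participant out of the study, not only off treatment. Two of them are "An adverse event which requires discontinuation of the study medication or results in inability to continue to comply with study procedures" and "Disease progression which requires discontinuation of the study medication or results in inability to continue to comply with study procedures".
- **The same section** commits to intention-to-treat: "Analysis of all participants who have been randomised will be undertaken regardless of withdrawal". It also has the reason for withdrawal recorded in the CRF.
- **Section 8.1** makes ferric maltol the study treatment and says of the other arm: "The control group will receive standard care only".
- **Section 9.2** describes an adverse-event stop as leaving treatment. The investigator may remove the participant from treatment, or: "A participant may also voluntarily withdraw from treatment due to what he or she perceives as an intolerable AE". It continues: "If either of these occurs, the participant will undergo an end of study assessment". It does not say when that assessment takes place or what it contains.
- **Section 7.7** places the final bloods and the three quality-of-life questionnaires at the 8–12 week clinic. For patients seen earlier, "then the usual 8-12 week outpatient visit will still be used". Withdrawn patients are not mentioned.
- **Section 8.8** keeps poor compliers in: "If there is a high level of non-compliance (<70%), the patient will be included in the trial under the intention-to-treat-analysis".
- **Section 10.3.2** lists withdrawal, compliance, retention and completion of outcome measures as separate primary feasibility measures.
- **Appendix 1** has no early-withdrawal column. It lists a withdrawal checklist whose content is not given.

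**The concern.** A rule that turns a drug stop into a study exit can act only where there is a study drug. Followed literally, it ends scheduled follow-up for some ferric maltol participants, possibly those who tolerated the drug least, and has no counterpart for controls.

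The outcomes at risk are those that need the participant to attend: haemoglobin, haematinics, SF36, EQ-5D and FACT-An at 8–12 weeks. Length of stay and transfusion can probably be recovered from the hospital and transfusion records named as source documents in section 11.1.

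This matters in a feasibility trial because sections 3.3.1 and 10.2 use the data to choose the sample size and outcome measures of a definitive trial. Retention and completion of outcome measures are also among the primary measures. Under the present rule both fall whenever the drug is stopped for one of these reasons, even if the participant would have been willing to attend.

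**Working it through.** **1. The plan's own figure.** Section 10.1 gives 20 per arm, and 20 + 20 = 40, as stated. There is no power calculation, dropout allowance or stopping rate to reproduce. The check is mainly a comparison of the text.

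**2. Who each part of the rule can reach.**

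| Part of the 7.8 criteria | Ferric maltol | Control |
|---|---|---|
| Adverse event or progression requires study medication to stop | yes | no (no study medication, 8.1) |
| Adverse event or progression prevents compliance with procedures | yes | yes |

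Only the first row is one-sided.

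**3. What follow-up the visible text gives after each type of departure from treatment.**

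| Situation | Status | 8–12 week bloods and questionnaires |
|---|---|---|
| Interruption, then restart (8.5) | stays in | yes, by schedule |
| Compliance under 70% (8.8) | stays in the intention-to-treat analysis | yes, by schedule |
| Stop for adverse event | out of the study (7.8), off treatment (9.2) | not stated; end of study assessment, timing and content unstated |
| Stop for progression | out of the study (7.8) | not stated; no assessment given |

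The last two rows cannot be squared with an analysis of everyone randomised for outcomes measured at that visit. A participant who takes few capsules is followed; one whose capsules are stopped for an adverse event is withdrawn.

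**4. Cost per withdrawal.** Section 10.3.2 does not define the retention denominator, so three are shown.

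- Randomised to the arm: 1/20 = 5.0 points.
- Whole trial: 1/40 = 2.5 points.
- Starters only, assuming 15 of 20 start treatment: 1/15 = 6.7 points.

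The 15 is 0.75 × 20. It borrows the 75% still anaemic at operation after intravenous iron (section 1). That is a weak proxy, because it precedes surgical blood loss. Each figure is an upper limit, since some who stop might have been lost anyway.

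**5. Illustrative counts.** The stopping rate f is assumed; the documents give none. With n starting treatment, the expected number is n × f and P(at least one) = 1 − (1 − f)^n.

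| f (assumed) | n = 20: expected | n = 20: P(≥1) | n = 15: expected | n = 15: P(≥1) |
|---|---|---|---|---|
| 5% | 1.0 | 1 − 0.95^20 = 0.642 | 0.75 | 1 − 0.95^15 = 0.537 |
| 15% | 3.0 | 1 − 0.85^20 = 0.961 | 2.25 | 1 − 0.85^15 = 0.913 |
| 30% | 6.0 | 1 − 0.70^20 = 0.999 | 4.5 | 1 − 0.70^15 = 0.995 |

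Within this range at least one such withdrawal is more likely than not. The range is a choice, not a finding.

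**The case against.** The case for leaving the text alone has several parts.

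- **Section 9.2 does provide for adverse-event stops.** Section 4 describes the final visit as bloods plus questionnaires, so an end of study assessment might naturally be read as the same content. That is fair as to content. Timing remains open, because the assessment is tied to the stop, so its data may be off schedule. Progression is not covered.
- **Progression may be rare.** Section 6 requires curative-intent surgery and excludes confirmed liver or lung metastases, and follow-up is about 12 weeks. The documents give no rate either way.
- **The cause is visible in reporting.** Reasons are recorded, and withdrawal, compliance and retention are listed separately. This stands. The feasibility counts can be explained; the unmeasured outcomes cannot be recovered that way.
- **The affected group is limited.** Interrupted treatment may restart, and poor compliers stay in. This also stands.
- **Some material is not visible.** The flow chart and the checklist content are not shown and might address follow-up. They could not remove the difference in wording between 7.8 and 9.2.
- **The analysis is descriptive, with no feasibility threshold (3.3.1, 10.2).** No stated decision rule is affected.

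A reader might go further and infer that ferric maltol retention will be worse than control, or that the haemoglobin effect will be inflated. The documents support neither. The inability-to-comply part and the other criteria act in both arms, so the net gap is unknown. No stopping rate or outcome difference is given, and section 10.3.3 reports a median haemoglobin change, so a simple shift-in-mean calculation would not describe it.

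**Conclusion.** The point holds, with limits. Section 7.8 converts a medication stop for an adverse event or progression into study withdrawal, through a route that only the ferric maltol arm has. Section 9.2 describes the adverse-event case differently. No visible text keeps these participants to the 8–12 week bloods and questionnaires, so the commitment to analyse all randomised participants is not supported for haemoglobin, haematinics and quality of life.

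Each such withdrawal costs up to 5 points of arm retention if the denominator is the 20 randomised, or 6.7 if 15 start treatment. How many will occur is an assumption. What is at risk is outcome data, not the ability to report why people left. It would be too strong to say that nothing is collected after a stop, since section 9.2 may yield some data after adverse-event stops.

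The change should be made because the loss is avoidable and the remedy is cheap. The trial can still be reported without it.

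**What to change.** 1. In section 7.8, define two statuses: discontinued study medication, and withdrawn from follow-up. State that participants who stop medication remain in the study and are invited to the existing 8–12 week visit for bloods and questionnaires, unless they withdraw consent or cannot attend.
2. Reconcile sections 7.8 and 9.2, and state the timing and content of the end of study assessment and how it relates to the 8–12 week visit.
3. In section 10.3.2, report treatment discontinuation and study retention separately, by arm and with reasons, and state the retention denominator.
4. As a separate edit affecting both arms, change section 10.5. It first seeks recovery of the data, then allows a repeat blood sample, and excludes the participant from the trial if neither is possible. Exclusion conflicts with the all-randomised commitment in 7.8. A blood result that can be neither recovered nor repeated should be a missing value, with the participant kept in.

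None of this alters when or why medication is stopped. The cost is protocol and CRF wording through section 13.7, where the sponsor and study team decide whether the amendment is substantial, plus modest follow-up effort at an outpatient appointment that is already routine.
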